### 1.3. Schedule of Activities (SoA)

SP I – Screening		SP II – Prospective Baseline	SP III – Double-Blind Treatment				ET	Comments
Visit 1 procedures may be conducted over more than 1 day as long as all activities are completed within the allowable visit tolerance.								
Visit Number	1	2	3	4 a	5 a	6		
Month relative to randomization (V3)	*	**		1	2	3		
*Screening lasts from 3 to 30 days.
 
** Eligibility is determined between a minimum of 30 days and a maximum of 40 days. Investigators have up to 5 additional days, if needed, to schedule participant's Visit 3 appointment.
 
For scheduling purposes, a month is 30 days.

Interval allowance (days)			-	±2	±2	±2		
Telephone Visit				X	X			See footnote a.
Informed consent	X							The ICF must be signed before any protocol-specific tests or procedures are performed.
Inclusion and exclusion, review and confirm	X	X	X					
Demographics	X							
Medical history	X							
Substance use	X							Substances: alcohol, caffeine, nicotine, tobacco
Concomitant medications	X	X	X	X	X	X		
AE	X	X	X	X	X	X		Any events that occur after signing the ICF are considered AEs as defined in Section 10.3.
Physical Evaluation								
Height	X							
Weight	X							
12-lead ECG (local)	X					X	X	
ECGs should be collected prior to blood draws. Participants should be supine for approximately 5 to 10 minutes before ECG collections and remain supine but awake during the ECG collection.
 
See Section 8.2.3 for additional details.

Vital signs	X		X			X	X	Includes body temperature, sitting blood pressure, and pulse.

SP I – Screening		SP II – Prospective Baseline	SP III – Double-Blind Treatment				ET	Comments
Visit 1 procedures may be conducted over more than 1 day as long as all activities are completed within the allowable visit tolerance.			1	2	3	4 a	5 a	6
Visit Number	1	2						
Month relative to randomization (V3)	*	**		1	2	3		
*Screening lasts from 3 to 30 days.
 
** Eligibility is determined between a minimum of 30 days and a maximum of 40 days. Investigators have up to 5 additional days, if needed, to schedule participant's Visit 3 appointment.
 
For scheduling purposes, a month is 30 days.

Interval allowance (days)			-	±2	±2	±2		
Telephone Visit				X	X			See footnote a.
								Blood pressure and pulse will be measured in triplicate after participant has been sitting for at least 5 minutes, and prior to blood draws.
Physical examination	X							

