6.4. WINDOWING CONVENTIONS

The following describes assignment of visit windows to the following data for purposes of analysis:

- Screening lasts from 3 to 30 days, approximately.
- Eligibility is determined between a minimum of 30 days and a maximum of 40 days.
- For scheduling purposes, a month is 30 days.

See Section 18.1.1. for the derivation of diary time periods. No other assignment of visit will be done – visit as collected will be used.

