17.1. DERIVATIONS

Diary compliance at each period is calculated as:

$$\frac{\text{Actual number of diary days in the period} * 100}{\text{Expected number of diary days in the period}}$$

Expected number of Diary days is calculated as date of injection at the end of interval minus date of injection at the beginning of the interval +1.

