A 50% responder (Participant with $\geq 50\%$ reduction from baseline in migraine headache days): is defined as Yes, if any participant who has a $\geq 50\%$ reduction in the total number of migraine headache days in a 30-day period relative to baseline period, as No if otherwise. Therefore, if the percent change from baseline in the number of migraine headache days is $\geq 50\%$, the participant will be counted as an 50% responder.

Change from baseline in the number of monthly migraine headache days in each 30-day period will be summarized from daily data for each patient in that period (including approximately 30 days of daily data from the baseline period prior to randomization, 3 months of daily data during double-blind treatment period).

The daily ePRO data will reflect whether the patients meet the migraine / probable migraine criteria; those data will be aggregated, and the number of migraine headache days will be provided for each of the 30-day periods.

18.1.2. ADJUSTING FOR THE NUMBER OF DAYS WITH NON-MISSING DIARY DATA IN THE PERIOD:

In calculating the number of migraine headache days for each period, if the period is not equal to 30 days, the number of migraine headache days will be adjusted by multiplying the number of migraine headache days by $(30/x)$ where “x” is the total number of non-missing diary days in the period.

This approach to missing ePRO diary data assumes that the rate of migraine headaches per day is the same with missing and non-missing ePRO diary days, and it is missing at random. The same approach will also be applied to secondary and exploratory measures that are derived from the ePRO data.

Additionally, if the ePRO compliance rate (please refer to Section 17) for a monthly interval is $\leq 50\%$, then all endpoints to be derived from the ePRO diary data for that one-month period will be considered missing. For a participant who discontinued early in the double-blind treatment

Document: **CCI**

Author: **PPD**

Version Number:

3.0

Version Date:

19May2023

CCI

phase, compliance rate for the last month of that study period will be calculated with the denominator of the maximum of 30 and the total number of calendar days in that month.

Secondary and Exploratory Migraine and Headache Measures

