Number of migraine headache days with acute (abortive) medication use is calculated as the number of calendar days in a 30-day period on which migraine or probable migraine occurs and acute (abortive) medication is used (based on the response to question 12 in the daily diary questions, Table G).

Weekly migraine headache days is defined as is calculated as the number of migraine headache days in a 7-day period on which a migraine headache occurs. For each month, the first 7 calendar days will be counted as week 1, the second 7 calendar days will be counted as week 2, the third 7 calendar days will be counted as week 3, and the rest of days will be counted as week 4.

Number of migraine headache hours is calculated as the total number of headache hours in a 30-day period on days when a migraine or probable migraine occurs.

Number days with acute (abortive) medication use is calculated as the number of calendar days in a 30-day period on which an acute (abortive) medication is used (based on the response question 12 in the in the daily diary questions, Table G).

Number of headache days is calculated as the number of calendar days in a 30-day period on which a headache occurs (includes migraine, probable migraine, and non-migraine).

Number of moderate to severe headache days is calculated as the number of calendar days in a 30-day period on which a headache occurs with a moderate or severe severity (based on Q3 response, Table G.)

Number of migraine attacks per 30-day period is calculated as the number of sets of consecutive days with migraine or probable migraine separated by at least one migraine-free day. For example, a migraine or probable migraine starting on 5JAN and ending on 6JAN will result in a migraine/probable migraine-free day on 7JAN (assuming that there is no migraine/probable migraine on 7JAN). This will count as 1 migraine attack that started on 5JAN and ended on

Document: **CCI**

Author: **PPD**

Version Number:

3.0

Version Date:

19May2023

CCI

6JAN. For a migraine attack that begins in one 30-day period but ends in another, only 1 migraine attack will be counted in the first of the 2 periods. For example, in the case of 7 days of consecutive migraine/probable migraine headache with 3 days in the baseline period and 4 days in Month 1, only 1 migraine attack will be counted in the baseline period; the 4 days of migraine/probable headache in Month 1 will not be counted as a migraine attack in Month 1.

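### The weekly migraine-day measure is defined per 7 days, but Week 4 takes all the days left in the month (9 of 30), with no rule that restores a 7-day count and no weekly baseline

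*SAP*

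**What the plan says.** The weekly measure is defined in SAP section 18.1.2, under the subheading for secondary and exploratory migraine and headache measures. It is the "number of migraine headache days in a 7-day period on which a migraine headache occurs". The first and second weeks are 7 calendar days each, "the third 7 calendar days will be counted as week 3", and "the rest of days will be counted as week 4".

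Just above this, the same section adjusts counts when a period is not 30 days long. The count is multiplied by 30/x, where x is the number of non-missing diary days in the period. The SAP adds: "The same approach will also be applied to secondary and exploratory measures that are derived from the ePRO data". It does not say whether x is counted per week or per month for a weekly measure, and it gives no 7/x version.

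SAP section 6.2 normalizes the baseline to 30 days. No section defines a baseline for a weekly count.

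The weekly measure feeds two additional exploratory endpoints in SAP Table D: change in weekly migraine headache days (MMRM) and weekly 50% response (GLIMMIX). The footnote to that table defines weekly onset as the first week in which galcanezumab is superior and stays superior for the remaining weeks of that month.

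**The concern.** A measure whose stated unit is 7 days is built from windows of unequal length. In any month other than one of 28 days, Week 4 does not fit its own definition. A longer window collects more migraine days at the same daily rate, so Week 4 can look worse than Weeks 1 to 3 when nothing has changed. For a responder endpoint, a longer window also makes it harder to stay at or below half of a 7-day baseline.

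The text allows more than one derivation, so two programmers could produce different Week 4 results from it. What is at stake is the level of Week 4 and how the week-by-week profile reads: an apparent loss of effect late in the month could come from the calendar rule alone.

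**Working it through.** **Inputs from the documents**
- Unit of the measure: 7 days; Weeks 1 to 3 together use 21 days (SAP 18.1.2).
- Nominal month: "For scheduling purposes, a month is 30 days" (SAP 6.4).
- Visit windows: ±2 days at Visits 4, 5 and 6 (Protocol 1.3).
- Diary interval for compliance: "date of injection at the end of interval minus date of injection at the beginning of the interval +1" (SAP 17.1). SAP Appendix 3 also treats a month as a dosing interval in its diary-compliance deviation.
- Eligible baseline: 4 to 14 migraine headache days (Protocol 5.1).

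The SAP gives no expected weekly figure, so there is none to reproduce.

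**Assumptions not in the documents:** weekly baseline = monthly baseline × 7/30; days independent at a constant daily rate; the true reductions stated below.

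**Step 1. Length of Week 4 = month length − 21**
- 30-day month: 30 − 21 = 9 days; 9/7 = 1.286, so 28.6% more days than the other weeks.
- Dosing intervals, Month 1 (28 to 32 days): 7 to 11 days.
- Dosing intervals, Months 2 and 3 if both bounding visits shift (26 to 34 days): 5 to 13 days.

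**Step 2. Expected unscaled count = daily rate × days**
- Constant 8 days per 30: 8/30 × 7 = 1.87 in a 7-day week; 8/30 × 9 = 2.40 in Week 4.
- Baseline 9 with a true halving (4.5/30 per day): 1.05 against 1.35. The 7-day baseline is 2.1, so the change is −1.05 in a 7-day week and −0.75 in Week 4.

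**Step 3. Unscaled 50% response = P(count ≤ 0.5 × baseline × 7/30), true halving**
- Baseline 8: the threshold is 0.93, so the count must be 0. The daily rate is 4/30. Over 7 days, (26/30)^7 = 36.7%. Over 9 days, (26/30)^9 = 27.6%.
- Baseline 12: the threshold is 1.4, so the count must be 0 or 1. The daily rate is 6/30 = 0.2. Over 7 days, 0.8^7 + 7 × 0.2 × 0.8^6 = 57.7%. Over 9 days, 0.8^9 + 9 × 0.2 × 0.8^8 = 43.6%.

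Averaged with equal weight over baselines 4 to 14:

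| True reduction | 7-day week | 9-day Week 4 |
|---|---|---|
| 45% | 50.4% | 38.8% |
| 50% | 54.8% | 43.5% |
| 55% | 59.4% | 48.5% |

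The loss is about 11 points. For a 5-day Week 4 the direction reverses: 68.1% against 54.8% at a true halving.

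**Step 4. Does the 30/x rule repair it?**
- With x counted per month, all four weeks get the same factor and the 9-to-7 imbalance stays.
- With x counted per week, each week becomes a 30-day rate, not a 7-day count. Expected values are then comparable across weeks and with the 30-day baseline.
- The per-week version does not repair the responder endpoint, because counts are integers. For a 9-day week at baseline 8, count × 30/9 ≤ 4 means count ≤ 1.2, so 0 or 1 qualifies. The response becomes 0.276 × (1 + 9 × 4/26) = 65.8%, against 36.7% for a 7-day week. At baseline 12, count × 30/9 ≤ 6 means count ≤ 1.8, so still 0 or 1, and the response stays at 43.6% against 57.7%.
- A 7/x factor gives the same thresholds and so the same responder results.

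**Step 5. Effect on the comparison between arms**

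With true reductions of 55% and 45%, the unscaled response difference averaged over baselines 4 to 14 is 9.0 points over 7 days and 9.8 points over 9 days (from unrounded rates).

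**The case against.** The strongest reply is that the SAP already extends its length adjustment to exploratory diary measures. If that is applied week by week, with the baseline on the same 30-day scale, expected Week 4 counts are not inflated. This stands for the mean count. The inflation is therefore conditional on no per-week scaling, and a reader who infers that Week 4 counts will certainly be overstated goes further than the text allows. The reply does not rescue the stated 7-day unit, does not supply a weekly baseline, and does not make the responder endpoint comparable (Step 4).

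A reader might also infer that Week 4 always has at least 9 days. That is not supported. It is exactly 9 in a fixed 30-day month, and it can be shorter or longer if months follow dosing intervals.

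A third tempting inference is that the rule damages the weekly onset claim, because onset must hold through Week 4. Onset is a comparison between arms within each week, and both arms have the same rule. Neither is favored under the null. In the worked example the arm difference is slightly larger over 9 days, not lost. The between-arm difference in mean counts is stretched by 9/7 on the unscaled reading, but the variance of the count also grows with the window. The documents do not show that the onset claim breaks.

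Finally, the weekly endpoints are exploratory, outside the testing hierarchy of SAP section 7.4, and tied to months in which galcanezumab was superior. That stands and limits the importance of the point.

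**Conclusion.** The point holds as a defect in the definition of the weekly measure. Its unit is 7 days, Week 4 has 9 days in a 30-day month, the 30/x rule does not give a 7-day count, and the weekly baseline is undefined.

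If Week 4 is not scaled per week and is set against a 7-day baseline, its expected count is 28.6% too high. Its 50% response is then lower by 9.1 points at baseline 8 (36.7 − 27.6) and 14.1 points at baseline 12 (57.7 − 43.6). These sizes rest on a true halving, independent days and a weekly baseline of monthly × 7/30. Clustering of migraine days into attacks would change them.

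The distortion lies in the level of Week 4 and in its comparison with Weeks 1 to 3. The primary and key secondary diary endpoints use 30-day periods and are untouched. This is a minor point, worth correcting because the correction is cheap.

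**What to change.** Before unblinding, amend the weekly definition in SAP section 18.1.2 as follows:

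1. Week 4 is days 22 to 28 of each month, so that all four weeks have 7 days.
2. The weekly baseline is the 30-day-normalized baseline × 7/30.
3. Where diary days are missing within a week, the count is multiplied by 7/x, with x the non-missing diary days in that week. This factor is used for nothing else.
4. The 30/x rule does not apply to weekly measures.

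If months follow dosing intervals, one that ends before day 28 leaves Week 4 short. The SAP should say that the absent days are handled as missing diary days.

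Keeping a 9-day Week 4 and scaling it by 7/x is not an adequate substitute. It corrects the mean count, but at baseline 8 it replaces a 9.1-point understatement of response with a 29.1-point overstatement (65.8 − 36.7), and at baseline 12 it changes nothing. The same integer effect remains in weeks with missing diary days, which is a reason to confine 7/x to them.

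The cost is a few SAP sentences and the related programming, with no new data. The downside is that days after day 28 of each month are not used in the weekly exploratory analyses; they stay in the monthly endpoints.

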18.1.3. MIDAS (MIGRAINE DISABILITY ASSESSMENT) QUESTIONNAIRE

The Migraine Disability Assessment questionnaire (MIDAS) consists of 5 questions (Q1-Q5) and 2 additional questions (A and B). The questionnaire measures the impact that migraine headaches have on migraineurs' life, including days of work or school missed, days with productivity at work or school reduced to half or more, days with household work missed, days with productivity in household work reduced to half or more, and days missed family / social / leisure activities. Each question is answered as a numeric number of days during the past 3

Document: **CCI**

Author: **PPD**

Version Number:

3.0

Version Date:

19May2023

CCI

months of assessment, ranging from 0 to 90. The answers to all 5 questions will be added up to a total MIDAS score. No imputation is needed when calculating the total score as participants are not allowed to send partial data. The answers to all 5 questions will be added up to a total MIDAS score. The total MIDAS score and item scores will be analyzed.

18.1.4. MIGRAINE SPECIFIC QUALITY OF LIFE (MSQ) v2.1

Migraine Specific Quality of Life (MSQ) v2.1 consists of 14 questions. The questions measure the impact of migraine on health-related quality of life across 3 domains: 1) Role Function-Restrictive (7 questions), examines the degree to which performance of daily activities is limited by migraine; 2) Role Function-Preventive (4 questions), examines the degree to which performance of daily activities is prevented by migraine; 3) Emotional Function (3 questions), examines feelings of frustration and helplessness due to migraine.

Precoded item values and final item values for each MSQ item response are shown in Table I. All item values range from 1 to 6. Final item value will be used as for analysis with higher score reflecting better quality of life.

Table I: Item Values for Migraine Specific Quality of Life (MSQ) Item Responses

Response Categories	Precoded Item Value	Final Item Value
None of the time	1	6
A little bit of the time	2	5
Some of the time	3	4
A good bit of the time	4	3
Most of the time	5	2
All of the time	6	1

Questions 1 to 7 of the questionnaire will be grouped together as Role Function-Restrictive domain, questions 8 to 11 as Role Function-Preventive domain and questions 12 to 14 as the Emotional Function domain. In general, no imputation for missing values is necessary because the MSQ was collected using participant direct data entry on an electronic device which did not allow participants to skip items. Participant either completed the scale in its entirety or not at all.

The raw score of each domain will be calculated as the sum of the raw scores of each question in that domain. The total score will be calculated as the sum of raw scores of Role Function-Restrictive, Role Function-Preventive, and Emotional Function domain scores.

Document: **CCI**

Author: **PPD**

Version Number:

3.0

Version Date:

19May2023

CCI

. If any of the 3 domain scores is missing, then total score will be missing.

In addition, the raw scores of each domain and the total score will be transformed to a 0 to 100 scale using the following formulae:

- Role Function-Restrictive (range of 7 to 42):

$$\frac{(\text{raw score} - 7) \times 100}{35}$$

- Role Function-Preventive (range of 4 to 24):

$$\frac{(\text{raw score} - 4) \times 100}{20}$$

- Emotional Function (range of 3 to 18):

$$\frac{(\text{raw score} - 3) \times 100}{15}$$

- Total Score (range of 14 to 84):

$$\frac{(\text{raw total score} - 14) \times 100}{70}$$

18.1.5. TOTAL PAIN BURDEN

Total pain burden: The total pain burden for a given month (severity-weighted duration) was calculated by multiplying duration (hours) of migraine headache and maximum pain severity (0 = none, 1 = mild, 2 = moderate, 3 = severe) for each migraine headache day and summing these over the days in a month. Total pain burden for a given month to be adjusted for 30 day period for a month as defined section 18.1.2.

18.1.6. PATIENT GLOBAL IMPRESSION

The Patient Global Impression of Severity (PGI-S): In this single-item scale, participants rate the severity of their migraine condition on a scale ranging from “not at all ill” (coded as 1) to “extremely ill” (coded as 7).

Change from baseline in PGI-S scores will be analyzed.

Document: CCI

Author: PPD

Version Number:

3.0

Version Date:

19May2023

CCI

18.2. PRIMARY EFFICACY

18.2.1. PRIMARY EFFICACY VARIABLE(S) & DERIVATION(S)

The primary endpoint is the percentage of participants with $\geq 50\%$ reduction from baseline in monthly migraine headache days across the 3-month double-blind treatment period. Please refer to Section 18.1.1 for derivations.

18.2.2. MISSING DATA METHODS FOR PRIMARY EFFICACY VARIABLE(S)

For the repeated measures analyses, the model parameters are simultaneously estimated using restricted likelihood estimation incorporating all of the observed data. Estimates have been shown to be unbiased when the missing data are missing at random.

Please refer to Section 18.1.2 for approach of handling missing diary data for derivation of the number of migraine headache days and other efficacy measures derived from ePRO data per 30-day period.

18.2.3. PRIMARY ANALYSIS OF PRIMARY EFFICACY VARIABLE(S)

The primary objective of this study is to assess whether galcanezumab is superior to rimegepant in the prevention of migraine in participants with episodic migraine. The primary estimand of interest is the overall mean monthly 50% response rate across the 3-month double-blind period attributable to the randomized treatment based on all available data as estimated from the model based on GLIMMIX-procedure. All available monthly migraine headache data will contribute to analysis as long as baseline monthly migraine headache day values are available. Any migraine headache day data collected after study intervention discontinuation but within the double-blind period will still be used within the analysis.

The primary efficacy analysis will be performed for the ITT. This endpoint (50% responder) is binary variable with repeated measures and will be analyzed using a GLIMMIX procedure as pseudo-likelihood-based mixed effects repeated measures analysis. The GLIMMIX procedure will include the fixed, categorical effects of treatment, month, and treatment-by-month interaction, as well as the continuous, fixed covariate of baseline monthly migraine headache days value. Binary distribution and logit link will be used.

An unstructured covariance structure will be used to model the within-participant errors (denoted by TYPE=CHOL in the RANDOM statement). The Newton-Raphson method with ridging will

Document: **CCI**

Author: **PPD**

Version Number:

3.0

Version Date:

19May2023

CCI

be used for nonlinear optimization (denoted by including NLOPTIONS TECH=NRRIDG). The Kenward-Roger (Kenward and Roger 1997) approximation will be used to estimate denominator degrees of freedom. If the model does not converge, the Fisher scoring algorithm will be utilized by the SCORING option in SAS.

If the model still fails to converge, the model will be fit using covariance matrices in the following order specified by a decreasing number of covariance parameters until convergence is met:

- Heterogeneous Toeplitz,
- Heterogeneous autoregressive,
- Toeplitz, and
- Autoregressive.

If necessary, both fitting algorithms will be used in the pre-specified order before proceeding to the next covariance structure in the sequence.

For models where the unstructured covariance matrix is not utilized, the sandwich estimator (Diggle et al. 1994) will be used to estimate the standard errors of the fixed effects parameters. The sandwich estimator is utilized by the EMPIRICAL option in SAS. When the sandwich estimator is utilized, the Kenward-Roger approximation for denominator degrees of freedom cannot be used. Instead, the denominator degrees of freedom will be partitioned into between-subject and within-subject portions by the DDFM=BETWITHIN option in SAS.

For the repeated binary efficacy measure where the objective is to assess the proportion of patients with 50% response during the 3-month double-blind treatment phase, the endpoint for comparing galcanezumab with rimegepant will be estimated as the treatment main effect from the categorical MMRM analysis assessing the response rate across Months 1, Month 2 and Month 3.

